Patients who provide informed consent will undergo screening evaluations to determine eligibility. Informed consent must be obtained within the 28 days prior to the first administration of study drug. Screening assessments will be initiated and completed within the 15 days prior to the first dose of study drug (except for radiology assessments, see Section 5.6).

In the Phase 2a portion of the study patients with recurrent glioblastoma must have evaluable disease, defined by contrast-enhancing MRI, within 15 days prior to starting study drug.

BAL101553 capsules will be given to fasted patients once or twice daily (depending on observed pharmacokinetics and clinical safety), continuously, until disease progression, unacceptable toxicity, or another reason for withdrawal from study drug occurs (see Section 4.4). A treatment cycle will be defined as one 28-day treatment period; there will be no treatment-free interval between treatment cycles.

Administration

Oral as hard capsules.

Phase 1 dose escalation portion (enrollment completed)

The starting daily dose of BAL101553 in patients with advanced or recurrent solid tumors was 2 mg/day BAL101553 (corresponding to approximately 1 mg/m²), based on Good Laboratory Practice (GLP) toxicology studies. Dose cohorts comprised three patients per cohort, unless a drug-related DLT was observed in any patient, at which point the cohort was expanded [up] to six patients. For all cohorts, dose increments between cohorts, ranging from 30–100%, were based on the extent and severity of observed drug toxicity.

Patients with recurrent or progressive GBM or high-grade glioma are analyzed as part of a separate dose-escalation scheme. The starting dose for the first GBM/glioma cohort was 8 mg/day and was based on the observed clinical safety in completed solid-tumor patient dose cohorts.

Dose escalation was performed in fasted patients using an accelerated 3+3 titration design (see Table 3 and Section 3.1.2.1). Details of the dose escalation process are provided in Section 3.2.1 (including intrapatient dose escalation). DLT definitions are provided in Section 3.2.2. The starting dose rationale is described in Section 1.5.3.

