1.3.2.1 Intravenous pharmacokinetics

After IV administration of the pro-drug, the conversion into the active BAL27862 amounts to between 35% and 61% in mice, rats, and dogs. Conversion of pro-drug is rapid, with a half-life ranging from 0.1-2 h. In animals BAL27862 has a large volume of distribution, a moderate-to-high metabolic clearance. and half-lives ranging 2.0-5.3 h in animals. Administration of pro-drug or drug leads to distribution into all tissues, notably tumor and brain; tumor retention is observed to be longer after administration of the pro-drug. In contrast to the increase in systemic exposure observed upon administration of increasing drug doses in mouse xenograft models, tumor exposure does not change, which is most likely due to the additional antivascular effects of the drug at higher doses. The mass-balance of both IV BAL27862 and BAL101553 is complete, with predominant elimination in the feces. Urinary excretion of both drug and pro-drug as unchanged drug is < 1%.

After repeated IV administration of BAL27862 or BAL101553 to mice, rats and dogs, the exposure is almost dose proportional, without indication of a gender effect, accumulation or induction.

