1.5.2.2.3 Surgical cohort

If futility is rejected in stage 1 of the Phase 2a Simon's two-stage design in patients with EB1-positive recurrent GBM, tumor tissue levels of BAL27862 will be determined in an additional cohort of up to 6 patients with planned re-resection of recurrent GBM. Details of this Surgical cohort will be provided in a separate protocol amendment pending the results of a non-clinical study in a rabbit animal model to assess any potential effects of BAL101553 on wound healing.

The physicochemical properties of BAL27862 (the active moiety of BAL101553) and available data in rodents from an autoradiography study ((Schmitt-Hoffmann 2009) suggest that BAL27862 penetrates the brain in a 1:1 ratio compared to plasma. The brain penetration of BAL27862 is further supported by central nervous side effects that were consistently observed in clinical studies at high exposures with BAL101553 such as visual hallucinations which were reversible within a few days, consistent with the plasma half-life of BAL27862 which is in a range of 12–24 hours.

However, a definitive assessment of the brain penetration of BAL27862 in humans is considered important, prior to entering a potential Phase 3 program in GBM. Therefore, it is planned to initiate a Surgical cohort in patients undergoing planned re-resection of recurrent GBM once an initial proof of concept has been achieved regarding the efficacy of BAL101553 in patients with EB1-positive GBM in the Stage 1 of the Simon's two-stage Phase 2 a expansion portion of study CDI-CS-002, and once pre-clinical data from a wound-healing study are available. The data from a pre-clinical wound-healing study are considered important, considering that BAL27862 has shown vascular disrupting effects when using dose regimens that result in high Cmax levels, i.e when using a 2-hour infusion regimen.

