3.1.1 Treatment cycles

Each treatment cycle will comprise 28 days of continuous, daily oral BAL101553 administration to patients in a fasted state. Section 3.2.6 describes the planned treatment duration.

Treatment may be administered on an inpatient or outpatient basis.

In the Phase 1 dose-escalation portion of the study, patients will be replaced if the minimum safety evaluation requirements for assessment of the MTD in Cycle 1 have not been met (see Sections 3.1.2 and 4.5).

In the Phase 2a dose expansion portion of the study, patients with measurable disease at baseline will be replaced if they could not complete at least one post-baseline RANO assessment after at least 6 weeks of study treatment (see Sections 3.1.3 and 4.5).

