There will be a minimum period of observation of 28 days from the first dose of the last patient treated at that dose level, to the first dose of the first patient treated at the next dose level. There will be a minimum period of observation of 7 days between the first doses given to the first and second patients in the cohort. No delay is required between the second patient and any subsequent patient enrolled at the same dose level. A delay in the start of the second cycle by more than 14 days due to a drug-related AE is considered a DLT. Therefore, no patients will be permitted to enroll in a new dose cohort until all patients in the current dose cohort have started treatment in Cycle 2, or have discontinued the study for reasons other than drug-related toxicity.

Recommendations for dose delays or dose modifications in patients experiencing BAL101553-related toxicities, are described in Section 3.2.5.2.

7E 11 4	T	1 4	• , •
Table 4	I I ASA	escalation	criteria
IADICT	17030 1	cocaration	CIIICIIA

Number of patients with treatment-related DLT in the first 3 patients of a dose cohort 1	Escalation decision
0 of 3 patients with DLT	Enroll 3 patients at the next dose level ² .
1 of 3 patients with DLT	• Enter 3 additional patients at this dose level.
	- If 0 of these 3 patients (total of 1 of the 6 patients) experience DLT, enter 3 patients at the next higher dose level ² .
	-If ≥ 1 of these 3 patients (total of ≥ 2 of the 6 patients) experience DLT, then dose escalation is stopped, and this dose is declared the MAD. At least 3 additional patients must be enrolled at the next lowest dose level ² if only 3 patients were treated previously at that dose, to determine the MTD.
≥ 2 of 3 patients with DLT	Dose escalation must be stopped. This dose level will be declared the MAD. At least 3 additional patients must be enrolled at the next lowest dose level ² if only 3 patients were treated previously at that dose, to determine the MTD.

Maximum administered dose (MAD):

The MAD is the dose level with a rate of DLT in \geq 33% of patients during treatment Cycle 1, i.e.:

- \geq 2 of [up to] 3 patients with DLT in the first 3 patients of a dose cohort.
- \geq 2 of [up to] 6 patients with DLT in a cohort that was expanded to 6 patients.

Maximum tolerated dose (MTD):

The MTD is the highest dose level below the MAD with an acceptable tolerability profile, i.e.:

• Not more than 1 of 6 patients with DLT at the highest dose level below the MAD.

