HNSTD (highest non-severely toxic dose) is defined as the highest dose level that does not produce evidence of lethality, life-threatening toxicities or irreversible findings.

Table 14 Calculation of the human starting dose based on the HNSTD in rodent (rat) and non-rodent (dog) species

Animal species	10% of HNSTD (mg/kg/day)	Conversion factor ¹ of animal doses (mg/kg) to human doses (mg/m ²)	Calculated human starting dose (mg/m²)
Male rat	1	6	6
Female rat	0.5	6	3
Male or female dog	0.33	20	6.6

¹Based on "Guidance for Industry: Estimating the Maximum Safe Starting Dose in Initial Clinical Trials for Therapeutics in Adult Healthy Volunteers Guidance for Industry and Reviewers U.S. Department of Health and Human Services, Food and Drug Administration Center for Drug Evaluation and Research (CDER), July 2005 Pharmacology and Toxicology"

Step 2: Human pharmacokinetic data from intravenous BAL101553

As shown in Table 15, the average half-life of BAL27862 (active drug) was dose-independent and the overall half-life ($t_{1/2}$) across doses was approximately 15 h, which corresponds to a calculated accumulation factor of 1.5 for a daily administration.

In animals after daily oral dosing of BAL101553 no accumulation of BAL27862 was observed. However, this is explained by the much shorter half-life of BAL27862 in animals (i.e., $t_{1/2}$ of 4 to 5 h in dogs for the highest dose group in the 4-week oral pivotal study, CDI-TOX-025).

Therefore, rather than a starting dose of 3 mg/m², which would be suggested based on the HNSTD in female rats (see Table 14), a daily oral dose of 2 mg/m² is suggested when considering the accumulation factor.

Table 15 Mean (SD) pharmacokinetic parameters of BAL27862 in study CDI-CS-001

BAL101553 dose (mg/m ²)		BAL27862	
(number of patients treated at the	Cmax	AUClast	t _{1/2}
respective dose level)	(ng/mL)	(ng·h/mL)	(hours)
15 (n=1)	154	1830 (7.07)	17.1 (1.67)
30 (n=4)	224 (68.7)	2500 (652)	15.9 (3.18)
45 (n=3)	413 (12.5)	5970 (1360)	16.8 (8.48)
60 (n=10)	479 (139)	6940 (4340)	15.8 (5.58)
80 (n=7)	615 (104)	7790 (3220)	12.8 (3.77)

Step 3: Expected bioavailability and first-pass hepatic effect of oral BAL101553

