6.4 Pharmacokinetic analysis

6.4.1 Pharmacokinetic Parameters

PK parameters for BAL101553 and BAL27862 will be calculated from the concentration-time data using a non-compartmental analysis (NCA) method in Phoenix WinNonlin (Version 8 or higher) using Plasma Model 200 - 202 with extravascular dosing or Urine Model. Actual elapsed sampling times relative to time of study drug administration will be used for all parameter estimations.

The following parameters will be derived, as data permit, for Day 1 of Cycles 1 and 2:

C_{max}	Maximum observed concentration
t_{max}	Time to reach maximum observed concentration
AUC_{0-t}	Area under the concentration-time curve from the time of dose administration to the last quantifiable concentration, calculated by linear-log trapezoidal rule
$AUC_{0-\tau}$	Area under the concentration-time curve over a dosing interval, calculated by linear-log trapezoidal rule
$AUC_{0-\infty}$	Area under the concentration-time curve from the time of dose administration extrapolated to infinity, calculated by linear-log trapezoidal rule
$t_{1/2}$	Terminal half-life, calculated as $\ln(2)/\lambda_z$, where λ_z is the terminal phase rate constant
CL/F	Apparent total body clearance (BAL101553 only)
V_z/F	Apparent total volume of distribution (BAL101553 only)
AR	Accumulation ratio, calculated as Cycle 2 Day 1 $AUC_{0-\tau}$ /Cycle 1 Day 1 $AUC_{0-\tau}$
Ae	Total amount of drug excreted in urine over 24 hr
Fe	Fraction of dose excreted in urine over 24 hr

Only data points that describe the terminal elimination log-linear decline will be used in the regression equation for calculation of λ_z . C_{max} and any data point in the distribution phase will not be included in the calculation of λ_z . A minimum of 3 points will be used for determination of the terminal elimination phase rate constant. A time interval of at least 1 half-life will be required to calculate λ_z . An adjusted r^2 value > 0.80 will be considered acceptable for the calculation of the terminal elimination phase rate constant. If adjusted r^2 falls below 0.80, or the above conditions are not met, then the terminal elimination phase rate constant and the associated values of $t_{1/2}$, $AUC_{0-\infty}$, CL/F , and V_z/F will be flagged. If the extrapolated $AUC_{0-\infty}$ is more than 20%, then $AUC_{0-\infty}$, V_z/F and CL/F will be flagged. Flagged values will not be included in the calculation of descriptive statistics.

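### AUC0-inf of BAL27862 on Cycle 2 Day 1 includes carry-over from earlier doses, and the accumulation ratio has no rule for reduced doses or dosing gaps (Phase 1, descriptive PK)

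*SAP*

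**What the plan says.** SAP 6.4.1 opens its parameter list with "The following parameters will be derived, as data permit, for Day 1 of Cycles 1 and 2". The list is the same for both days. AUC0-inf is defined as "Area under the concentration-time curve from the time of dose administration extrapolated to infinity, calculated by linear-log trapezoidal rule", and there is no separate rule for a steady-state profile. CL/F and Vz/F are marked as applying to BAL101553 (the pro-drug) only. The accumulation ratio is AUC0-tau on Cycle 2 Day 1 divided by AUC0-tau on Cycle 1 Day 1, with no condition on dose or on continuity of dosing.

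The same section flags AUC0-inf, CL/F and Vz/F when more than 20% of AUC0-inf is extrapolated, or when the terminal slope fails its criteria, one of which is a time window of at least one half-life. Flagged values are left out of the descriptive statistics. SAP 6.4.2 still lists individual values.

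On dosing, Protocol 3.1.1 says "Each treatment cycle will comprise 28 days of continuous, daily oral BAL101553 administration to patients in a fasted state", and the synopsis and Protocol 5.3.2 say "there will be no treatment-free interval between treatment cycles". On kinetics, Protocol 1.5.2.2.3 describes reversible side effects as "consistent with the plasma half-life of BAL27862 which is in a range of 12–24 hours". Appendix 1 says that the BAL27862 half-life "across doses was approximately 15 h, which corresponds to a calculated accumulation factor of 1.5 for a daily administration".

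SAP 3.2.2 lists CL/F and Vz/F under a heading that covers both BAL101553 and BAL27862. Protocol 5.7.1 likewise promises clearance and volume for BAL27862. SAP section 7 declares no changes from the protocol's planned analysis.

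**The concern.** After a single dose, AUC0-inf measures the exposure from that dose. At steady state the same calculation measures that exposure plus whatever earlier doses left behind. The one-dose exposure at steady state is AUC0-tau. Reporting AUC0-inf for both days under one name gives two different quantities, and under linear kinetics the second is larger by construction. A reader of the listings could take the difference for a change in the drug's kinetics on repeated dosing.

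The accumulation ratio has a related weakness. It reads as accumulation only if the patient took the same dose without a gap up to Cycle 2 Day 1. Protocol 3.2.5.2 allows a Phase 1 patient to resume at a lower dose level and allows Cycle 2 to start up to 14 days late. Protocol 3.2.7 lets patients continue after missed doses. In such patients the ratio mixes accumulation with dosing history.

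**Working it through.** **Inputs.** Dosing interval 24 h (Protocol 3.1.1). BAL27862 half-life 15 h (Appendix 1) and 12 to 24 h (Protocol 1.5.2.2.3). Pro-drug half-life from animal IV data (Protocol 1.3.2.1): "Conversion of pro-drug is rapid, with a half-life ranging from 0.1-2 h". Phase 1 sampling on Day 1 of Cycles 1 and 2 runs from pre-dose to 24 h, with a 72 h sample optional (Protocol 5.7.1.1). Linear one-compartment kinetics are assumed; Appendix 1 expects linearity.

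**The plan's own figure.** Let q = 2^(−24/t½), the fraction remaining after one interval. The accumulation factor is R = 1/(1 − q). At 15 h, q = 2^(−1.6) = 0.330 and R = 1/0.670 = 1.49, which agrees with the protocol's 1.5.

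**AUC0-inf at steady state.** AUC0-tau at steady state equals the one-dose AUC to infinity. The extrapolated tail is a share q of the total, so AUC0-inf = AUC0-tau/(1 − q) = R × the one-dose AUC.

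| Half-life | q (extrapolated share) | R | Overstatement of AUC0-inf | Dose/AUC0-inf relative to true CL/F (1/R) |
|---|---|---|---|---|
| 12 h | 0.25 | 1.33 | 33% | 0.75 |
| 15 h | 0.33 | 1.49 | 49% | 0.67 |
| 24 h | 0.50 | 2.00 | 100% | 0.50 |

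A non-compartmental calculation on a simulated oral profile at the Phase 1 sampling times (absorption rate 1 to 2 per h, an assumption) gave AUC0-inf ratios of 1.34–1.35, 1.51–1.52 and 2.02–2.03. Dose/AUC0-tau on Cycle 2 Day 1 recovered the true CL/F at all three half-lives.

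**Effect of the flag.** The extrapolated share reaches 0.20 when 2^(−24/t½) = 0.20, i.e. t½ = 24/log2(5) = 24/2.322 = 10.3 h. Values at 12 h or longer are flagged, on Cycle 1 Day 1 as well. At 24 h the terminal-slope window also fails, because routine sampling ends at 24 h and Cmax is excluded. Values that pass have R up to 1/(1 − 0.20) = 1.25.

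**Pro-drug.** At the longest documented half-life, 2 h, q = 2^(−12) = 0.0002 and R = 1.0002, so there is no material carry-over.

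**Accumulation ratio at 15 h.**

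- Same dose, no gap: 1.49.
- Steady state at 25 mg/day after starting at 30 mg/day (both levels appear in Table 22): 1.49 × 25/30 = 1.24.
- Three days without drug before Cycle 2 Day 1: 1 + q^4/(1 − q) = 1 + 0.0118/0.670 = 1.02.
- Delay of 14 days: 1.00.

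Dividing each AUC0-tau by its dose turns 1.24 back into 1.49, but only if the lower dose has itself reached steady state. If it is first taken on Cycle 2 Day 1, the raw ratio is 25/30 + q/(1 − q) = 0.833 + 0.492 = 1.33, and the normalised ratio is 1.33 × 30/25 = 1.59, which is too high.

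**The case against.** The case for leaving the text alone has real substance.

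First, a reader might infer that the plan understates clearance on repeated dosing. As 6.4.1 is written, it does not. CL/F and Vz/F are restricted to BAL101553, whose documented half-life leaves nothing after 24 h. The 0.50 to 0.75 factors above would apply only if BAL27862 clearance were derived as dose/AUC0-inf on Cycle 2 Day 1. That possibility stays open because SAP 3.2.2 and Protocol 5.7.1 list clearance for BAL27862.

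Second, the flag rules remove most inflated values from the summaries. This stands, but it is selection and not correction. The listings keep the flagged values, and any summary on Cycle 2 Day 1 would describe only patients with short half-lives, whose values are still too high by up to 25%.

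Third, AUC0-tau is already derived on both days, and Protocol 8.3.2.9 refers to a Pharmacokinetics Manual that may set steady-state conventions. The manual is not among the documents, and the SAP text does not defer to it on this point.

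Fourth, few patients may be affected in the ratio. Table 22 lists seven patients with DLTs among the 54 dosed (26 + 28). Dose increases cannot occur before Cycle 2 Day 1, because Protocol 3.2.5.1 requires two completed cycles. However, non-DLT events can also lead to reductions or delays. Protocol 3.1.2.2 says "A delay in the start of the second cycle by more than 14 days due to a drug-related AE is considered a DLT", so a shorter delay does not in itself make a DLT. The documents give no count of such patients.

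**Conclusion.** The point holds in a limited form. For BAL27862 in Phase 1, AUC0-inf on Cycle 2 Day 1 is the wrong quantity for one-dose exposure. It is too large by the accumulation factor, about 33% at a 12 h half-life and 49% at 15 h. In the summary tables the overstatement is at most 25%, in the subset that escapes the flag. The accumulation ratio can drop from 1.49 to about 1.24 or 1.02 for reasons unrelated to accumulation. These sizes rest on linear one-compartment kinetics and the protocol's half-lives; the statement that the pro-drug is unaffected rests on animal data.

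Two stronger readings are not supported. One is that the 25 mg/day choice is affected because it rests on an AUC threshold of 2375 h*ng/mL. The dose and the threshold are already fixed in the protocol, Appendix 3 does not say which day's AUCinf entered the model, and SAP 6.4 does not specify that model. The other is that Phase 2a results are affected. Protocol 5.7.1.2 takes only a pre-dose sample on Cycle 2 Day 1, so no AUC can be derived there, and the Phase 2a primary analysis does not use PK.

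**What to change.** Amend SAP 6.4.1 as follows.

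- Derive AUC0-inf, and any parameter calculated from it, for Cycle 1 Day 1 only.
- On Cycle 2 Day 1, report AUC0-tau as the exposure measure. If clearance is reported for that day, calculate it as dose/AUC0-tau, which needs no extrapolation.
- State for which analyte CL/F and Vz/F are derived, and make SAP 3.2.2 and 6.4.1 agree. If the restriction to BAL101553 stays, record it in SAP section 7 as a change from Protocol 5.7.1.
- Dose-normalise the accumulation ratio, or restrict it to patients on the same dose at both profiles. In either case, exclude or list separately patients with a recent interruption, a recent dose change or a late Cycle 2 start. A window of five days before Cycle 2 Day 1 would do: the effect of an earlier gap or change has then decayed to 2^(−120/15) = 0.4% at a 15 h half-life and 2^(−120/24) = 3% at 24 h.

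The cost is SAP wording and a steady-state setting in the non-compartmental analysis. No new samples are needed. The downside is that a few patients leave the ratio; the number excluded should be reported beside it.

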- Drug-related AE(s) in Phase 1 which lead(s) to missing greater than five doses within any 28-day cycle, or lead(s) to a delay of more than 14 days in the commencement of the subsequent cycle.
- Requirement for more than two dose level reductions in a patient.
- Recurrence of the same toxicity, with the same or worse severity, in a patient who had a dose reduction due to toxicity.
- Requirement for other anticancer therapy.
- Grade 4 hypertension.
- Recurrent QTcF > 500 ms or QTcF increase from baseline > 60 ms.
- Pregnancy

ASSESSMENTS OF:

SAFETY / TOLERABILITY

The severity of AEs will be described using the National Cancer Institute CTCAE v4.03 (Phase 1) and v5.0 (Phase 2a) criteria. Safety evaluations will include analysis of AEs, laboratory assessments (hematology, biochemistry, cardiac troponin, coagulation, urinalysis), pregnancy testing in women of childbearing potential, ECG, transthoracal echocardiography, chest X-ray (Phase 1)/computed tomography (CT)/MRI, vital signs, ECOG performance status, physical examination, and evaluation of concomitant medications.

PHARMACOKINETICS

PK variables calculated from plasma concentration data using noncompartmental analysis for BAL101553 (if applicable) and for BAL27862 will comprise: C_{max} , T_{max} , $AUC_{0-\tau}$, AUC_{0-last} , $AUC_{0-\infty}$, $t_{1/2}$, systemic clearance and volume of distribution.

Total 24-h urinary excretion of BAL101553 and BAL27862.

EFFICACY

Phase 1 dose escalation portion:

In patients with advanced or recurrent solid tumors, evaluation of disease progression and response in patients with measurable disease will be assessed by RECIST criteria v1.1. In patients with ovarian or prostate cancer with non-measurable disease, response will be evaluated by the CA-125 Rustin criteria or the PSA Working Group 2 criteria, respectively. For patients with recurrent or progressive GBM or high-grade glioma, evaluation of disease progression and response will be assessed by contrast-enhanced MRI, based on the RANO criteria. Clinical progression of the tumor disease will also be considered as progressive disease.

Phase 2a dose expansion portion (Simon's two-stage design):

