5.7.1 Blood samples for pharmacokinetic assessments

The following PK parameters will be determined for BAL101553 (if applicable), and for BAL27862: C_{max} , T_{max} , $AUC_{0-\tau}$, AUC_{0-last} , $AUC_{0-\infty}$, $t_{1/2}$, systemic clearance and volume of distribution

Detailed instructions and procedures for collecting and handling samples for PK analysis are provided in the 'BAL101553 Pharmacokinetics Manual' at the site.

If needed, the PK sampling schedule may be amended based on observed PK in humans, however, no more than ten PK samples will be obtained in order to establish a plasma concentration-time profile at Day 1 of Cycles 1 and 2.

Unless otherwise stipulated in the 'BAL101553 Pharmacokinetics Manual' at the site, the PK of BAL101553 and BAL27862 will be evaluated by analysis of blood samples collected.

5.7.1.1 Phase 1

Unless otherwise stipulated in the 'BAL101553 Pharmacokinetics Manual' at the site, the PK of BAL101553 and BAL27862 will be evaluated by analysis of blood samples collected:

- Day 1 of Cycles 1 and 2 at the following time points:
 - Pre-dose
 - 0.5 h, 1 h, 2 h, 3 h, 4 h, 6 h, 8 h and 24 h after dosing.
 - Open Depending on the observed PK during the dose escalation portion of the study, a sample at 72 h (Day 4) may also be obtained.
 - For cohorts using a q12h dosing regimen, a PK sample will be also be obtained at 12 h (i.e., prior to the second daily dose) after first dosing.
- Days 8, 15 and 22 of Cycles 1 and 2:
 - Pre-dose
- When a patient reports a DLT, a single blood sample for PK analysis should be obtained, if possible (date and time of blood sampling must be recorded in the CRF).
- At the End of Study visit, blood must be taken for determination of trough PK levels.
- In patients undergoing intra-patient dose escalation or dose reduction, additional blood PK samples must be collected on one dosing day at each new dose level for a given patient. These PK samples must be collected pre-dose, and 0.5 h, 1 h, 2 h, 3 h, 4 h, 6 h, 8 h and 24 h after dosing. For cohorts using a q12h dosing regimen, a sample will be also be obtained at 12 h (i.e., prior to the second daily dose) after first dosing.

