3.2.2 Secondary endpoints

Secondary endpoints are:

- Overall safety endpoints:
 - Type and frequency of AE, SAEs, laboratory, echocardiogram and Electrocardiogram (ECG) abnormalities; abnormalities in vital signs, physical examination results, chest X-ray/CT; frequency and causes of study withdrawals and dose modifications.
- Efficacy endpoints:
 - Best objective response according to Response Evaluation Criteria in Solid Tumors (RECIST) 1.1 in patients with solid tumors, based on the change from baseline in tumor measurements as measured in patients with measurable disease, and according to RANO criteria in patients with progressive or recurrent GBM or high-grade glioma (Phase 1 only).
 - PFS and OS.
- Pharmacokinetic assessments (BAL101553 and BAL27862):
 - C_{max} , t_{max} , AUC_{0-t} , $AUC_{0-\infty}$, AUC_{0-last} , $t_{1/2}$, systemic clearance (CL/F), volume of distribution (Vz/F), accumulation ratio.
 - Total 24-h urinary excretion of BAL101553 and BAL27862.

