7 CHANGES FROM THE PLANNED ANALYSIS IN STUDY PROTOCOL

Not applicable.

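### SAP 6.4.1 plans no clearance or volume summary for the active drug BAL27862, and its 20% extrapolation rule could thin the AUC0-inf summary to an unknown extent

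*SAP*

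**What the plan says.** **Analyte.** SAP 6.4.1 defines CL/F as "Apparent total body clearance (BAL101553 only", and puts the same restriction on Vz/F. SAP 3.2.2, under a line naming both BAL101553 and BAL27862, includes "systemic clearance (CL/F), volume of distribution (Vz/F), accumulation ratio". Protocol 5.7.1 introduces a list containing clearance and volume with "The following PK parameters will be determined for BAL101553 (if applicable), and for BAL27862". The synopsis agrees: "PK variables calculated from plasma concentration data using noncompartmental analysis for BAL101553 (if applicable) and for BAL27862 will comprise". Protocol 8.1 lists clearance and volume for both analytes. SAP section 7, headed "CHANGES FROM THE PLANNED ANALYSIS IN STUDY PROTOCOL", is marked as not applicable.

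**Exclusion rules.** SAP 6.4.1 sets the days: "The following parameters will be derived, as data permit, for Day 1 of Cycles 1 and 2". It flags AUC0-inf, CL/F and Vz/F if more than 20% of AUC0-inf is extrapolated. For the terminal slope it asks for at least 3 points, without Cmax, and an adjusted r² above 0.80, and adds: "A time interval of at least 1 half-life will be required to calculate" the slope. If a slope condition fails, t1/2, AUC0-inf, CL/F and Vz/F are flagged. The consequence of any flag is: "Flagged values will not be included in the calculation of descriptive statistics".

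**Sampling.** Dosing is daily without a break (protocol 3.1.1). Full profiles end at 24 h, on Day 1 of Cycles 1 and 2 in Phase 1 (5.7.1.1) and on Day 1 of Cycle 1 only in Phase 2a (5.7.1.2).

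**The concern.** Pharmacokinetics of BAL27862 is a secondary objective in both phases. If the SAP is followed literally, two parameters that the protocol requires for the active drug are not derived, and nothing records that they were dropped.

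The exclusion rule raises a second question. The protocol puts the BAL27862 half-life at 12–24 h, so a profile that stops at 24 h covers only one to two half-lives. A 20% limit may then sort patients by half-life, which is itself a PK result, as well as removing imprecise values. The AUC0-inf values left would come preferentially from patients with short half-lives. If clearance varies between patients, that summary is too low; if only volume varies, it is not biased in this way. The two matters are linked: removing the pro-drug restriction alone would place BAL27862 CL/F and Vz/F under the same 20% rule.

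**Working it through.** **Part 1: the analyte.** No arithmetic applies. The protocol makes BAL27862 the unconditional analyte and BAL101553 the conditional one; SAP 6.4.1 reverses this for CL/F and Vz/F. SAP 3.2.2 and 6.4.1 also disagree with each other. Number of BAL27862 CL/F and Vz/F summaries planned under 6.4.1: none.

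**Part 2: the share extrapolated.** The documents state no extrapolated share, so there is no figure to reproduce.

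Inputs: last profile sample 24 h (protocol 5.7.1.1, 5.7.1.2); half-life t of 12–24 h (1.5.2.2.3), about 15 h on average (Appendix 1, Step 2); limit 20% (SAP 6.4.1).

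*Mono-exponential decline.* Share beyond 24 h: e = 2^(−24/t).
- t = 12 h: 2^(−2) = 25%
- t = 15 h: 2^(−1.6) = 33%
- t = 24 h: 2^(−1) = 50%
- Longest half-life that passes: 24 × ln 2 / ln 5 = 10.3 h, below the stated range

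At steady state on Cycle 2 Day 1, AUC0-24 = A and the tail is A·e/(1−e), so the share is again e.

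*With an early phase.* If an early phase carries a fraction f of AUC and is nearly finished by 24 h, the share is about (1−f)·e. To pass, f must be at least 1 − 0.20/e: 20% at 12 h, 39% at 15 h, 60% at 24 h.

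Protocol Table 15 (2 h infusion) gives some indication of f. With R = AUClast/Cmax, mono-exponential decline predicts R = 2/(1 − 2^(−2/t)).

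| Dose, mg/m² | t, h | R observed, h | R expected, h |
|---|---|---|---|
| 15 | 17.1 | 1830/154 = 11.9 | 26 |
| 30 | 15.9 | 2500/224 = 11.2 | 24 |
| 45 | 16.8 | 5970/413 = 14.5 | 25 |
| 60 | 15.8 | 6940/479 = 14.5 | 24 |
| 80 | 12.8 | 7790/615 = 12.7 | 19 |

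The shortfall means an early phase, a truncated AUClast, or both. Taking AUClast as complete and assuming an early half-life h, f = (2/R − b)/(a − b), with a = 1 − 2^(−2/h) and b = 1 − 2^(−2/t). Example, 30 mg/m² and h = 4 h: f = (0.179 − 0.084)/(0.293 − 0.084) = 0.46, and the share is 0.54 × 0.351 + 0.46 × 0.016 = 20%. Across the five rows:
- h = 2 h: 23–32%
- h = 4 h: 20–27%
- h = 6 h: 13–23%

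Overall the share is about 13–32%, on both sides of the limit.

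*Sensitivity by simulation.* Planned sampling times and SAP rules were applied with an assumed mean half-life of 12–18 h (SD 3.8–5.6 h), absorption rate about 1 per h and 10% residual error. Without an early phase, 69–98% of AUC0-inf values are excluded. At a mean half-life of 15 h, with an early phase of half-life 3 h carrying 10%, 20% or 30% of AUC, exclusion is 76%, 50% or 10%.

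**Part 3: t1/2.** The slope window ends at 24 h. Its length is 24 − 6 = 18 h for the last three points, 24 − 3 = 21 h from 3 h, and 24 − 2 = 22 h if Cmax falls at 1 h. Half-lives above about 18–22 h would therefore be flagged. That is the upper part of the 12–24 h range, but above every dose-level mean in Table 15 (12.8–17.1 h).

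**The case against.** - **The restriction may be deliberate.** CL/F refers to the administered compound, and BAL101553 is what is dosed. That is a tenable choice, but then SAP 3.2.2 is wrong and section 7 should say so. A reader might also infer that the SAP plans these parameters for an analyte that cannot be measured. The documents support this only in animals, where at most traces of pro-drug were found in plasma after oral dosing (protocol 1.3.2.2); they do not say whether it holds in patients.
- **Most AUC0-inf values will be lost.** This inference is tempting from the 25–50% shares, but it depends on mono-exponential decline. SAP 6.4.1 itself allows for a distribution phase, Table 15 is compatible with one, and exclusion falls to 10% under one plausible assumption. The last sampling time behind Table 15 is not given, so neither reading can be confirmed.
- **The accumulation factor of 1.5 in Appendix 1 might seem to confirm a 33% share.** It is calculated from the same 15 h half-life, so it adds no independent evidence.
- **Excluding poorly extrapolated values is a legitimate prespecified quality rule.** This stands. Individual values are listed and n is reported (SAP 6.4.2), so exclusions would be visible. It does not remove the selection by half-life.
- **The Pharmacokinetics Manual may say more.** Protocol 8.3.2.9 refers the detailed PK analysis to it, and it may change sampling times. It is not among the documents. Under daily dosing no later sample can extend a single-dose profile past 24 h; the optional 72 h Phase 1 sample follows further doses.
- **The tables might seem unfit for comparison with the AUCinf analysis in protocol Appendix 3, which plots all Phase 1 patients.** A summary after exclusions would indeed not match it directly, but no passage plans that comparison.

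**Conclusion.** The analyte conflict is firm and rests on the text alone: as written, the SAP omits CL/F and Vz/F of the active drug, which the protocol requires, and declares no change.

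The extrapolation point is conditional. The share beyond 24 h is 25–50% if decline is mono-exponential, and about 13–32% with an early phase consistent with Table 15, assuming a complete AUClast and an early half-life of 2–6 h. A substantial fraction of BAL27862 AUC0-inf values could therefore be excluded, preferentially in patients with long half-lives, together with t1/2 values above about 18–22 h. Neither the number excluded nor the size of any bias can be established, because the human oral profile is not in the documents.

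The effect is confined to descriptive PK tables. Cmax, AUC0-t, AUC0-tau and the individual listings are untouched, and no stage or dose decision uses these tables.

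**What to change.** 1. In SAP 6.4.1, delete the restriction to BAL101553 and derive CL/F and Vz/F for BAL27862. In Phase 1, base CL/F on AUC0-tau from Cycle 2 Day 1, where a full profile exists. Under linear kinetics at steady state this AUC equals the single-dose AUC0-inf and needs no extrapolation, so the SAP should also state that the 20% flag does not apply to it. If the restriction is intended, declare it in SAP section 7 and correct SAP 3.2.2.
2. Report BAL27862 AUC0-inf, t1/2, CL/F and Vz/F with and without flagged values, with counts and the percentage extrapolated. Make this change together with the first.
3. In Phase 2a, where Cycle 2 Day 1 has only a pre-dose sample, show the flagged Cycle 1 values marked as less precise.

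The cost is SAP wording and minor programming, with no new samples. The drawback is that the all-patient tables will contain less precise values; the parallel tables and the percentage extrapolated make this visible.
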